#### 4.3.1.1   Solicited Reactions

##### 4.3.1.1.1   Daily Intensity

All daily records for solicited reactions will be derived into daily intensity according to the following classification: None, Grade 1, Grade 2, Grade 3, or Missing (Unknown).

For the derivation of daily intensities, the following sequential steps will be applied:

- 1) Solicited reactions (except Fever/Pyrexia) with eCRF presence recorded as "No" and with all daily records missing (Unknown) then all daily intensities will be derived as None.
- 2) For a temperature partially missing after decimal point, the data will be analyzed replacing "MD" (missing data) by zero. For example, a "39.MD" daily temperature will be considered as "39.0°C" at the time of analysis.
- 3) For non-measurable solicited reactions, daily intensities will correspond to daily records reported in the clinical database. For measurable solicited reactions the daily measurements reported in the clinical database will be converted based upon the intensity scales defined in the protocol; this assumes a reaction that is too large to measure (non-measurable, "NM") is Grade 3. Note the intensity could be considered "None" (not a reaction) in the analysis despite being considered a reaction by the investigator (eg, swelling measurement  $> 0$  mm but  $< 25$  mm in subjects aged  $\geq 12$  years).

Note: The maximum intensity on the ongoing period is derived from the record of the maximum intensity/measurement after the end of the solicited period following the rule described above.

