#### 4.3.1.1.3 Presence

Presence is derived from the maximum overall intensity over the time period considered:

- None: No presence
- Grade 1, Grade 2, or Grade 3: Presence
- Missing or Unknown: Missing presence

Subjects with at least one non-missing presence for a specific endpoint will be included in the analysis. Conversely, those without a non-missing presence will not be included in the analysis of the endpoint.

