#### 4.3.1.1.7 Ongoing

Ongoing is derived from the last daily intensity of the solicited period computed as described in [Section 4.3.1.1.1](#) and the maximum intensity on the ongoing period. The investigator’s ongoing flag is not used because the measurement would determine the ongoing status of the reaction.

- Ongoing: if the last daily intensity of the solicited period is at least Grade 1 and the maximum intensity on the ongoing period is at least Grade 1
- Not ongoing: if the last daily intensity of the solicited period is None or the maximum intensity on the ongoing period is None.
- Missing: all other conditions (in this case, it is not included in the denominator of the ongoing analysis in the safety tables).

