##### **4.3.1.3.6 Adverse Events Leading to Study Discontinuation**

Adverse Events Leading to Study Discontinuation are defined as AEs leading to discontinuation of the study during each active phase (primary series Cohort 1: from Visit 1 up to Visit 5; booster phase Cohort 1: from Visit 6 up to Visit 8; primary series Cohort 2: from Visit 1 up to Visit 4; booster phase Cohort 2: from Visit 8 up to Visit 10). AEs leading to discontinuation of the study during safety follow-up phase are not to be considered for this category.

This information will be summarized as collected. A flag is available in the clinical database for all AEs in order to identify AEs leading to study discontinuation before the end of each active phase.

In general, the items that are counted are:

- Disposition table: A subject who, on the “Completion at End of Study” form question “What was the subjects' status?” has “Adverse Event” checked.
- Safety overview table: A subject who has either on the “Completion at End of Study” form, question “What was the subjects' status?” has “Adverse Event” checked or lists a solicited AE that has “Caused Study Termination” checked that is at least Grade 1 or an unsolicited AE that has “Caused Study Discontinuation” checked that is at least Grade 1 or missing and is within the time period indicated.
- System Organ Class (SOC)/Preferred Term (PT) table: A solicited AE that has “Caused Study Termination” checked that is at least Grade 1 or an unsolicited AE that has “Caused Study Discontinuation” checked that is at least Grade 1 or missing and is within the time period indicated.

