### *Safety endpoint*

The analysis will be descriptive using the Safety Analysis Set (SafAS) in the primary series and the Safety Analysis Set for booster (SafASB), for each vaccination group. The statistics presented on [Table 5.1](#) will be produced.

The safety analysis will report the occurrence of solicited reactions and the incidence of unsolicited AEs, including SAEs and AESIs, over the safety observation period by age group and vaccine group according to the vaccine received.

- Immediate unsolicited systemic AEs reported in the 30 minutes after each vaccination
- Solicited injection site reactions occurring within 7 days after each vaccination
- Solicited systemic reactions occurring within 7 days after each vaccination
- Unsolicited injection site AEs occurring within 28 days after each vaccination
- Unsolicited systemic AEs occurring between each vaccination and up to 28 days after the last vaccination
- SAEs and AESIs throughout the study (until 6 months after last vaccination for the primary vaccination series and throughout the entire study for the subset of subjects included in the booster phase)

In order to avoid any under-estimation of the incidences, the number of subjects with documented safety will be used as denominator of the frequencies.

- For solicited reactions, the denominator is the total number of subjects who have non-missing data for the particular category of reaction during the time period concerned.

**Note:** for solicited systemic reactions, if a reaction is ongoing at the time of the next vaccination, it will be treated differently depending on whether or not it has increased in intensity following the later vaccination.

- If it has not increased in intensity after the next vaccination, it is to be attributed to the earlier vaccination, and is counted as just a single occurrence in safety analysis. The time of onset is the first day of the first occurrence in the earlier vaccination.

- If it has increased in intensity after the next vaccination, it will be counted as 2 separate occurrences after each vaccination in safety analysis (the 2 occurrences will be attributed to the earlier vaccination and later vaccination, respectively). The date of the later vaccination will be considered as the end date for the first occurrence and the start date of the second occurrence, respectively.

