#### **5.3.2.4 Intensity**

For solicited reactions, missing intensities will be handled as described in [Section 4.3.1.1.1](#). For unsolicited AEs, missing intensities will remain missing and will not be imputed.

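### Solicited reactions recorded as present but never graded are dropped, while ungraded absences are kept, which pulls most solicited-reaction rates slightly down

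*SAP*

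**What the plan says.** SAP 4.3.1.1.1 derives daily intensity in sequential steps. Step 1 covers solicited reactions other than fever whose eCRF presence is No: such a reaction "and with all daily records missing (Unknown) then all daily intensities will be derived as None". No step mentions presence Yes. Step 3 then governs what is left: "For non-measurable solicited reactions, daily intensities will correspond to daily records reported in the clinical database", with measurable reactions converted through the protocol's size scales.

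SAP 4.3.1.1.2 takes the maximum of the daily intensities. SAP 4.3.1.1.3 turns a Missing maximum into missing presence. It includes subjects who have at least one non-missing presence for the endpoint, and adds: "Conversely, those without a non-missing presence will not be included in the analysis of the endpoint". SAP 5.3.2.4 sends solicited reactions back to 4.3.1.1.1 and adds no rule of its own.

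Under Safety endpoint in SAP 5.1.2.2 the purpose of the denominator is given: "In order to avoid any under-estimation of the incidences, the number of subjects with documented safety will be used as denominator of the frequencies".

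Unsolicited AEs are handled differently. SAP 4.3.1.2.1 counts an event that has a verbatim term and is not Grade 0. SAP 5.3.2.4 states: "For unsolicited AEs, missing intensities will remain missing and will not be imputed". Their intensity table has a Missing row, whereas the solicited maximum-intensity list stops at Grades 1 to 3. In the SOC/PT discontinuation table of SAP 4.3.1.3.6, an unsolicited AE qualifies at Grade 1 or above or with grade missing. A solicited one qualifies only if "checked that is at least Grade 1 or an unsolicited AE that has" and so on, that is, only with a recorded grade.

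**The concern.** The same kind of evidence, a site answer without diary grades, is accepted when negative and discarded when positive. Subjects known not to have reacted stay in the denominator. Subjects known to have reacted leave both numerator and denominator.

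Describing safety after each injection is a stated secondary objective, and solicited reactions are a secondary endpoint. A rule that removes known reactors and keeps known non-reactors lowers the very rates the study is meant to describe, and works against the reason the SAP gives for its choice of denominator.

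**Working it through.** The documents state no expected solicited-reaction rate and no rate of ungraded records, so there is no figure of the plan's own to reproduce. The check is a trace of the rule, followed by algebra under an assumed share of ungraded reactors.

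**Trace: one reaction, one dose, all daily records missing**

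- Presence No: step 1 sets every day to None, the maximum is None, there is no presence, and the subject is in the denominator.
- Presence Yes: step 1 does not apply and step 3 carries the missing records through. The maximum is Missing, presence is missing, and the subject is out of the endpoint. SAP 5.1.2.2 agrees, since its denominator is subjects with non-missing data for that reaction.

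**Direction**

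Let a = subjects with Grade 1 or higher recorded, b = subjects with None recorded, c = No with all records missing, d = Yes with all records missing.

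- SAP rate = a/(a+b+c)
- Rate counting the recorded Yes = (a+d)/(a+b+c+d)
- Second minus first = d(b+c)/[(a+b+c)(a+b+c+d)], which is positive whenever d > 0 and b+c > 0.

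This holds where a Yes implies at least Grade 1: pain or tenderness, systemic reactions other than fever, and erythema or swelling below 12 years, where any size above 0 mm is Grade 1 (Protocol Tables 9.1 and 9.2).

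**Size**

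Let p be the true rate and m the share of reactors with no graded day (an assumption; the documents give none). The SAP reports p(1−m)/(1−pm).

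| p | m = 2% | m = 5% | m = 10% |
|---|---|---|---|
| 10% | 9.8% | 9.5% | 9.1% |
| 30% | 29.6% | 28.9% | 27.8% |
| 50% | 49.5% | 48.7% | 47.4% |

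For example, at p = 30% and m = 5%: 0.285/0.985 = 28.9%.

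In whole subjects, take the 303 planned for VRVg-2 in one Cohort 1 age group (SAP Table 3.1), with 30 reactors of whom 3 have no grades. The true 30/303 = 9.9% is reported as 27/300 = 9.0%.

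**Why the one-sidedness matters**

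Suppose the same share m is ungraded among Yes and No subjects. Dropping both gives p(1−m)/[p(1−m)+(1−p)(1−m)] = p, which is unbiased. Keeping only the No subjects gives p(1−m)/[p(1−m)+(1−p)] = p(1−m)/(1−pm), the table above.

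**Tables after any injection**

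Because one non-missing presence is enough for inclusion, a subject with an ungraded Yes at one dose and None at another may be counted as having no reaction. If that happened to every such subject, the rate would be p(1−m): 30% would be reported as 29.4%, 28.5% or 27.0% at m = 2%, 5% or 10%. This is an outer case.

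**Erythema and swelling from 12 years**

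Grade 1 starts at 25 mm (Protocol Table 9.3), so an unmeasured Yes may be a non-reaction by scale. Dropping 3 such subjects from 30/303 gives 30/300 = 10.0%, up from 9.9%. The direction is not fixed here.

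**The case against.** The best defence is that such records should be rare. Protocol 13.2 has the coordinator clarify missing diary data with the subject, Protocol 11.2 applies systematic checks for omissions, and Protocol 12.3.1 expects very little missing safety data. A recorded No is also an answered item, so step 1 reads data that exist. The safety analysis is descriptive, the rule is the same in every arm, and no primary or key secondary test depends on it. All of that stands, and it limits the size. It does not supply the missing rule: a recorded Yes is just as much an answered item.

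One can also say that the denominator sentence in SAP 5.1.2.2 is about excluding undocumented subjects, which by itself raises rates. That is fair as far as it goes, but a subject with a recorded Yes is not undocumented.

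A reader might infer more than the documents support:

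- **That every solicited rate can only fall.** Fever is outside step 1. For erythema and swelling from 12 years, the lost Yes may be a non-reaction by scale and the rate can move up.
- **That SAP 4.3.1.1.7 has the same flaw.** It reads: "Not ongoing: if the last daily intensity of the solicited period is None or the maximum intensity on the ongoing period is None". Ongoing means present on the last solicited day and present afterwards, so a single None properly negates it. With the last day missing, the status is unknown, and calling it Ongoing could take in an onset after D7, which Protocol 9.2.1.1 treats as unsolicited.
- **That an ungraded solicited reaction ending participation disappears from all discontinuation tables.** The overview and disposition tables also count subjects through the Adverse Event status on the completion form, which Protocol 5.2.11 assigns to such subjects. Only the SOC/PT table can miss the event.
- **That a Yes with some days None and the rest missing within one dose is certainly counted as no reaction.** SAP 4.3.1.1.2 does not say how None and Missing combine, so that is only one possible reading.

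**Conclusion.** The concern holds in a limited form. As written, the SAP keeps ungraded non-reactors and drops ungraded reactors. For pain or tenderness, systemic reactions other than fever, and erythema or swelling below 12 years, the reported rate is biased downward as soon as one such Yes exists alongside any non-reactor.

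The size is unknown and probably small. At a true 30% the shortfall is about 0.4, 1.1 or 2.2 percentage points for an assumed 2%, 5% or 10% of reactors without grades; no document supports any particular share. The figures also take each recorded Yes to be a true reaction. Because the rule is common to all arms, the effect on the descriptive rates is clearer than any effect on contrasts between vaccines. This is a cheap improvement to the safety description and not a threat to the trial's conclusions.

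**What to change.** - In SAP 4.3.1.1.1 and 4.3.1.1.3, add that a solicited reaction with eCRF presence Yes and all daily records missing is counted as Presence with intensity Missing, and that the subject stays in numerator and denominator. Apply this to pain or tenderness, systemic reactions other than fever, and erythema or swelling below 12 years.
- For erythema and swelling from 12 years, where size decides presence, leave the record missing and report how many there are.
- Add a Missing row to the solicited maximum-intensity tables, as the unsolicited tables already have.
- In SAP 4.3.1.3.6, change only the solicited criterion of the SOC/PT table to at least Grade 1 or missing. Leave the overview and disposition tables and SAP 4.3.1.1.7 as they are.

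The cost is SAP wording and minor programming, with no new data. Reported reaction rates may come out slightly higher.

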##### 4.3.1.1.2   Maximum Overall Intensity

Maximum overall intensity is derived from the daily intensities computed as described in [Section 4.3.1.1.1](#) and is calculated as the maximum of the daily intensities over the period considered.

#### 4.3.1.1.3 Presence

Presence is derived from the maximum overall intensity over the time period considered:

- None: No presence
- Grade 1, Grade 2, or Grade 3: Presence
- Missing or Unknown: Missing presence

Subjects with at least one non-missing presence for a specific endpoint will be included in the analysis. Conversely, those without a non-missing presence will not be included in the analysis of the endpoint.

#### 4.3.1.1.4 Time of Onset

Time of onset is derived from the daily intensities computed as described in [Section 4.3.1.1.1](#). It corresponds to the first day with intensity of Grade 1, Grade 2, or Grade 3.

Note: If a reaction is not continuous (ie, reaction occurs over two separate periods of time intervened by at least one daily intensity Missing or None) then the time of onset is the first day of the first occurrence.

Note: for solicited systemic reactions, if a reaction is ongoing at the time of the next vaccination, it will be treated differently depending on whether or not it has increased in intensity following the later vaccination.

- If it has not increased in intensity after the next vaccination, it is to be attributed to the earlier vaccination, and is counted as just a single occurrence in safety analysis. The time of onset is the first day of the first occurrence in the earlier vaccination.
- If it has increased in intensity after the next vaccination, it will be counted as 2 separate occurrences after each vaccination in safety analysis (the 2 occurrences will be attributed to the earlier vaccination and later vaccination, respectively). The date of the later vaccination will be considered to be the end date for the first occurrence and the start date of the second occurrence, respectively.

#### 4.3.1.1.5 Number of Days of Occurrence During the Solicited Period

Number of days of occurrence over the period considered is derived from the daily intensities computed as described in [Section 4.3.1.1.1](#). It corresponds to the number of days with daily intensities of Grade 1, Grade 2, or Grade 3. Number of days of occurrence on the solicited period with a specified intensity may also be derived.

#### 4.3.1.1.6 Overall Number of Days of Occurrence

If a reaction is ongoing at the end of the solicited period, then the overall number of days of presence is derived from the daily intensities and the end date of the reaction after the end of the solicited period. The overall number of days of presence is:

- (End date - last vaccination date) + (number of days of presence within the solicited period) - length of the solicited period + 1

If the end date is missing or incomplete (contains missing data), the overall number of days of presence will be considered as “Missing”.

#### 4.3.1.1.7 Ongoing

Ongoing is derived from the last daily intensity of the solicited period computed as described in [Section 4.3.1.1.1](#) and the maximum intensity on the ongoing period. The investigator’s ongoing flag is not used because the measurement would determine the ongoing status of the reaction.

- Ongoing: if the last daily intensity of the solicited period is at least Grade 1 and the maximum intensity on the ongoing period is at least Grade 1
- Not ongoing: if the last daily intensity of the solicited period is None or the maximum intensity on the ongoing period is None.
- Missing: all other conditions (in this case, it is not included in the denominator of the ongoing analysis in the safety tables).

#### 4.3.1.2 Unsolicited AEs (Including SAEs and AESIs)

##### 4.3.1.2.1 Presence

An observation will be considered an event if it has at least a verbatim term and is not a Grade 0 intensity event.

Grade 0 events should not be included in safety analysis but are included in the separate listing “Unsolicited adverse events not included in the safety analysis.”

##### 4.3.1.2.2 Intensity

Intensity for unsolicited AEs will be derived according to the following classification: Grade 0 (None), Grade 1, Grade 2, Grade 3, or Missing

If the unsolicited AE is measurable and its preferred term is part of the list of solicited reactions, then the measurement is derived based upon and following the same rule of the intensity scales defined in the protocol for that measurable injection site or systemic reaction. Note the intensity could be considered as “None” (not a reaction) in the analysis despite being considered a reaction by the investigator (eg, swelling measurement  $> 0$  mm but  $< 25$  mm in subject aged  $\geq 12$  years).

Intensity for the other unsolicited AEs will correspond to the value reported in the eCRF.

The maximum intensity corresponds to the highest intensity for a unique term.

#### **4.3.1.2.3 Last Vaccination**

Last vaccination before an unsolicited AE is derived from the start date of the unsolicited AE provided in the eCRF and is calculated as follows:

- If an unsolicited AE has a complete start date and different to any of the vaccination dates, the start date is used to determine the last vaccination before the unsolicited AE
- If the start date is missing or partially missing, or equal to any vaccination date, then the visit number in the “Appeared after Visit” or similar field, is used to determine the last vaccination before the unsolicited AE

#### **4.3.1.2.4 Time of Onset**

Time of onset is derived from the start date of the unsolicited AE and the date of last vaccination as described in [Section 4.3.1.2.3](#):

- Time of Onset = start date of the unsolicited AE – date of last vaccination before the unsolicited AE

The time of onset is considered as missing only if one or both dates are missing or partially missing.

An unsolicited AE with missing time of onset will be considered to have occurred just after the last vaccination (computed according to the [Section 4.3.1.2.3](#)), so will be included in the safety analysis.

**Note:** Unsolicited AE that occurred before vaccination (negative time of onset) will not be included in analysis but will be listed separately.

#### **4.3.1.2.5 Duration**

Duration is derived from the start and end dates of the unsolicited AE:

- Duration = end date of unsolicited AE – start date of unsolicited AE + 1.

The duration is considered as missing only if one or both of the start and end dates of the unsolicited AE is missing or partially missing.

#### **4.3.1.2.6 Serious Adverse Events**

An event will be considered as a serious event if “Yes” is checked for “Serious” in the eCRF.

#### **4.3.1.2.7 Adverse Events of Special Interest**

An unsolicited event will be considered as an AESI if “Yes” is checked for “Is the event an AESI?” in the eCRF.

#### **4.3.1.3 Other Safety Endpoints**

##### **4.3.1.3.1 Pregnancy**

This information will not be included in the analysis but will be listed separately. No derivation or imputation will be done.

##### **4.3.1.3.2 Action Taken**

This information will be summarized as collected, including missing observations. No derivation or imputation will be done.

##### **4.3.1.3.3 Seriousness**

This information will be summarized as collected. No derivation or imputation will be done.

##### **4.3.1.3.4 Outcome**

This information will be summarized as collected. No derivation or imputation will be done.

##### **4.3.1.3.5 Causality**

This information will be summarized as collected in the field “Relationship to investigational product”. Missing causal relationship to study vaccine (investigational product) will be handled as described in [Section 5.3.2.2](#).

Relationship to study procedure for SAE is only presented in the listing.

##### **4.3.1.3.6 Adverse Events Leading to Study Discontinuation**

Adverse Events Leading to Study Discontinuation are defined as AEs leading to discontinuation of the study during each active phase (primary series Cohort 1: from Visit 1 up to Visit 5; booster phase Cohort 1: from Visit 6 up to Visit 8; primary series Cohort 2: from Visit 1 up to Visit 4; booster phase Cohort 2: from Visit 8 up to Visit 10). AEs leading to discontinuation of the study during safety follow-up phase are not to be considered for this category.

This information will be summarized as collected. A flag is available in the clinical database for all AEs in order to identify AEs leading to study discontinuation before the end of each active phase.

In general, the items that are counted are:

- Disposition table: A subject who, on the “Completion at End of Study” form question “What was the subjects' status?” has “Adverse Event” checked.
- Safety overview table: A subject who has either on the “Completion at End of Study” form, question “What was the subjects' status?” has “Adverse Event” checked or lists a solicited AE that has “Caused Study Termination” checked that is at least Grade 1 or an unsolicited AE that has “Caused Study Discontinuation” checked that is at least Grade 1 or missing and is within the time period indicated.
- System Organ Class (SOC)/Preferred Term (PT) table: A solicited AE that has “Caused Study Termination” checked that is at least Grade 1 or an unsolicited AE that has “Caused Study Discontinuation” checked that is at least Grade 1 or missing and is within the time period indicated.

